The applicant proposes a prospective, randomized controlled open-label trial known as SUSTAIN, or **Stop Community MRSA Colonization among Patients**. The SUSTAIN trial will evaluate MRSA decolonization and determine differences in the prevalence of MRSA colonization (main outcome) at 6 months. Patients with a known history of MRSA colonization will be recruited from the (JHUAS). After consent and baseline MRSA screening, index subjects (50 per arm), described below, will be randomized to a standardized decolonization protocol directed at both the individual and their household and/or sexual partner(s) or a decolonization for the individual alone. Each index (i.e. person living with HIV within the Johns Hopkins Moore Clinic) will be approached for enrollment in the study. Information flyers, study rotating digital kiosk and provider referral will be used for recruitment. We will also search the Johns Hopkins Hospital Epidemiology and Infection Control (HEIC) database for known MRSA colonized individuals and contact former study participants.

SUSTAIN Standardized Decolonization Regimen (intervention):

According to the IDSA clinical practice guideline⁷, the standardized decolonization regimen for the nose and groin will include a 5-day course of nasal mupirocin calcium 2% cream applied inside the nose twice daily, plus a 4% chlorhexidine gluconate (soap) used in the shower/bath every day for 10 days^{20,19}. For individuals colonized within the throat we will add chlorhexidine gluconate oral rinse 0.12% used in a gargle and spit fashion twice daily for 7 days. A standardized educational session on use and accompanying CDC instructional frequently asked questions handout and an instructional medication sheet will be provided. For children < 7 years of age, we will provide decolonization using 4% chlorhexidine gluconate (soap) used in the shower/bath every day for 10 days. No antimicrobial cream or gargle will be utilized. If an adult household member or sexual partner is colonized at a single site, he or she will receive the soap, rinse and Mupiricin cream. If he/she is not colonized at any body site, no decolonization regimen will be provided.

Date: 6/10/13

Principal Investigator: [name], MPH, NP

Application Number: NA_00079147

ENROLLMENT:

Patient Population/Setting:

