Individuals, 21 years of age and older, of all racial and ethnic groups, receiving care within the JHUAS who have a prior history of MRSA colonization are eligible to participate as the index HIV positive subject. This person should have at least two members in the household and/or a sexual partner. A post-consent pre-randomization screening phase will be completed to ensure subjects are MRSA colonized. In addition to these criteria subjects must be willing to be randomized to either arm of the study, including randomization to household and/or sexual partner evaluation. Sexual partners and/or household members will also be required to provide informed consent. Subjects and their contacts must have no documented or reported allergies to any agent used in the standardized decolonization regimen. Parental assent will be required for household members less than 7 years of age. Exclusion criteria include: allergy to any component of decolonization protocol; individuals who live alone and have no active sexual partners; individuals who are unable to provide written informed consent.

Recruitment Strategy:

Study team members will speak with JHUAS providers to discuss the study and seek patient referrals (i.e. index patient). A HIPAA waiver will be sought in order to obtain a list of patients with a known history of MRSA colonization from Johns Hopkins Hospital Epidemiology and Infection Control Department. In the HIPAA waiver, we are asking to contact the patient's provider in the Moore Clinic to inform of the patient's eligibility for the study prior to the subject seeing his or her provider in clinic. The provider could then inform the patient of their eligibility and ask if we can contact them about the study. [name] previous work has already identified over 70 JHUAS patients with a known history of MRSA colonization. The patients in this prior study have agreed to be contacted for future studies when they signed informed consent. We have included details for a HIPAA waiver to evaluate this information in this IRB application. We have also

Date: 6/10/13

Principal Investigator: [name], MPH, NP

Application Number: NA_00079147

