completed a HIPPA form 3 to document that we have permission to contact the index patient again for future studies on MRSA in this patient population. These index HIV positive patients will be approached for study screening during a clinic visit or via telephone to schedule a study visit. Index HIV positive patients will receive a \$25.00 gift card on completion of the protocol. We will offer household members a single gift card of \$50.00 regardless of the number of participants.

Recruitment of Household Members/Sexual Contacts:

To avoid disclosure of personal health information (PHI), the index patient will be given the option for a home visit by the research team or they and their household members and sexual contacts can be screened at the Clinical Research Unit (CRU). We will work closely with the IRB/DSMB to protect subject's PHI. Recruitment of the primary sexual partner and or family members will occur by referral from the enrolled subject. During the risk factor evaluation, the subject will be asked, "In the last 6 months have you had sex?" We then ask several follow-up questions on sexual activity. The enrolled subject will be asked to refer his/her primary sexual partner, the person the subject most frequently engages in anal, vaginal or oral sex with, to the study. At no time will study data of either the primary subject or the subject's sex partner be shared by the research team to the other participant regardless of their awareness of the other partner's status. Neither the screening process, nor the questionnaire reveals any information about HIV status.

6. Drugs/Substances/Devices

According to the IDSA clinical practice guideline⁷, the standardized decolonization regimen for the adult colonized in either the nose or groin will include a 5-day course of nasal mupirocin calcium 2% applied inside the nose twice daily, plus a 4% chlorhexidine gluconate (soap) used in the shower every second day for 10 days²⁰. For individuals colonized within the throat we will add chlorhexidine gluconate oral rinse 0.12% used in a gargle and spit fashion twice daily for 7 days. A standardized educational session on use and accompanying instructional handout will be provided. Children under 6 months will not be included in the study. For children over 6 months and <7 years of age 4% chlorhexidine gluconate (soap) used daily for 10 days. For children over the age of 7, we will follow the same protocol as adults.

7. Study Statistics

ANALYSIS:

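### The adult chlorhexidine soap schedule is daily in Section 4 but every other day in Section 6: 10 uses against 5

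*Combined protocol and SAP*

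**What the plan says.** The soap instruction appears in two places in the combined protocol and SAP.

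- **Section 4 (Study Procedures, standardized regimen).** For the nose and groin, the regimen is a 5-day course of twice-daily nasal mupirocin "plus a 4% chlorhexidine gluconate (soap) used in the shower/bath every day for 10 days". Children under 7 have their own instruction: for those under 7 "years of age, we will provide decolonization using 4% chlorhexidine gluconate (soap) used in the shower/bath every day for 10 days". The section adds that "an instructional medication sheet will be provided".
- **Section 6 (Drugs/Substances/Devices).** This section gives "the standardized decolonization regimen for the adult colonized in either the nose or groin" as the same 5-day mupirocin course "plus a 4% chlorhexidine gluconate (soap) used in the shower every second day for 10 days". For children over 6 months and under 7 "years of age 4% chlorhexidine gluconate (soap) used daily for 10 days". For older children: "For children over the age of 7, we will follow the same protocol as adults".

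Section 5 defines the index population as "Individuals, 21 years of age and older, of all racial and ethnic groups, receiving care within the JHUAS" with a history of MRSA colonization, so every index subject is an adult.

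**The concern.** The two sections give different frequencies for the same product over the same 10 days, and the people they cover overlap. Staff who follow one section depart from the other.

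The soap is part of the study treatment for index subjects in both arms and for treated contacts in the household/partner arm. Several other parts of the plan assume a single prescribed regimen:

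- Section 7 (Limitations, loss to follow-up) has research assistants contact patients daily during decolonization to check fidelity to the regimen.
- Section 4 (Follow-up) schedules an adherence evaluation at Visit 1.
- Section 2 makes a fidelity assessment plan for a larger trial part of Aim 2.
- Section 8 requires a report to the IRB within 7 days when an adverse drug reaction leads to a breach of protocol. A participant who cuts back to alternate-day use because of skin irritation would breach Section 4 but comply with Section 6.

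**Working it through.** The plan states no total number of soap uses, so there is no figure of its own to reproduce. The check compares the texts and then counts days.

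**Step 1. Is it the same regimen?**

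| Feature | Section 4 | Section 6 |
|---|---|---|
| Guideline cited at the start | Reference 7 | Reference 7 |
| Described as standardized | Yes | Yes |
| Nasal mupirocin 2% | 5 days, twice daily | 5 days, twice daily |
| Soap | 4% chlorhexidine | 4% chlorhexidine |
| Soap period | 10 days | 10 days |
| Soap frequency, general/adult | Every day | Every second day |
| Throat carriage | Adds 0.12% oral rinse, twice daily for 7 days | Adds 0.12% oral rinse, twice daily for 7 days |
| Soap frequency, under 7 years | Every day | Daily |

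Within the soap instruction, frequency is the one substantive difference.

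**Step 2. Do the two texts cover the same people?** Section 4 treats children under 7 separately, so its general regimen covers adults. Section 6 names adults colonized in the nose or groin. Index subjects are 21 or older. An index subject colonized in the nose and groin therefore falls under both texts on any reading of the and/or wording. Children over 7 come in through Section 6, which places them on the adult protocol.

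**Step 3. Could one text be superseded or damaged?** Both are body text under the same protocol date, and both sentences are intact. No clause gives one section precedence.

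**Step 4. Size of the difference over days 1 to 10.**

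- Section 4: one use on each of 10 days = 10 uses.
- Section 6, first use on day 1: days 1, 3, 5, 7, 9 = 5 uses.
- Section 6, first use on day 2: days 2, 4, 6, 8, 10 = 5 uses.
- Ratio: 10 / 5 = 2.
- Days on which the sections disagree about whether soap is due: 10 − 5 = 5 of 10.
- Children under 7: 10 against 10, no conflict.

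**Step 5. Illustration for adherence.** The protocol does not define its adherence measure. Assume it is uses taken divided by uses planned. A participant who follows Section 6 exactly then scores 5 / 10 = 50% against Section 4.

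No total per arm or for the trial can be given, because the number of participants colonized in the nose or groin is not stated.

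**The case against.** The contradiction itself is hard to dispute. The objections concern its reach and weight.

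1. **Scope.** Section 6 names only adults colonized in the nose or groin, whereas screening also covers throat, rectum and vagina. For an adult colonized only in the rectum or vagina, Section 6 states no soap schedule, and for throat-only carriage the base regimen is implied rather than stated. This stands: the twofold figure should be read as applying to adults colonized in the nose or groin, and to children over 7 through the adult protocol.
2. **Citations.** Both sections open with the same guideline, but at the soap clause Section 4 cites references 20 and 19 and Section 6 cites only 20. That may hint at how the texts diverged, but it does not reconcile them.
3. **Delivery.** The instructional medication sheet is not among the documents and may carry one clear schedule that everyone follows. The documents cannot show that the conflict reaches participants. However, a sheet with one schedule can match only one of the two sections.
4. **Effect on the result.** The randomized contrast is who is treated, not how often soap is used. The sample size, endpoint and Fisher's exact test do not depend on soap frequency, and non-uniform delivery is not shown. This also stands, and it limits the point to whether the protocol can be carried out and its adherence judged.
5. **The 50% figure.** It rests on an assumed measure and restates the 5-to-10 ratio. It is an illustration and adds no weight.

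**Conclusion.** The concern holds, with high confidence. The protocol gives the soap component of its study treatment in two incompatible forms for overlapping people: 10 uses or 5 in the same 10 days. The count does not depend on the starting day, and the conclusion rests only on both sections being in force, as they appear to be.

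This must be corrected because a treatment rule stated two ways cannot be followed as written and leaves fidelity and adherence without one protocol standard. It is not a finding of bias in the primary comparison. No view is taken on which schedule is right.

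**What to change.** Reconcile Sections 4 and 6 so that one soap schedule for each age group appears in both, and make clear which colonized sites it covers. The investigators decide which schedule is intended. Then check that the instructional medication sheet, the daily contacts during decolonization and the Visit 1 adherence evaluation all use the reconciled text.

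The cost is a wording amendment and a check of the medication sheet and adherence procedures. Sample size, endpoint and analysis are unchanged.

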To assess colonization prevalence among PLWHA, we conducted an epidemiologic evaluation of MRSA among persons within the Johns Hopkins University AIDS Service (JHUAS). The study included 500 subjects (65.8 % male) along with the sexual partners of 35 subjects. The MRSA colonization prevalence was 16.8% among subjects and 37% (17/35) in their sexual partners (unpublished data). These findings demonstrate an exceptional difference in colonization prevalence in PLWHA compared to the US population¹⁰ and supports the need for further research to understand decolonization regimens that evaluate outcomes for individual decolonization only compared to the inclusion household and/or sexual partner interventions. We propose a randomized controlled trial (RCT) among 100 PLWHA (50 per arm) within the JHUAS to evaluate an individual versus household/sexual partner decolonization intervention.

2. Objectives/Aims

The specific aims of the proposed RCT are:

1. To compare a MRSA decolonization protocol for the colonized individual (index) versus the index plus their household member and/or routine sexual partner(s).
H0: Index plus household/sexual partner(s) decolonization will be associated with a lower occurrence of MRSA colonization at 6 months after completion of decolonization protocol.
2. To estimate the intervention effect size and develop an intervention fidelity assessment plan to scale the intervention into a larger multi-city R01 application.
3. To determine the molecular characteristics and antimicrobial susceptibilities of both the clinical and colonizing isolates among index patient as well as household members.

3. Background

Community-associated methicillin resistant *Staphylococcus aureus* (CA-MRSA) greatly impacts health outcomes among PLWHA. Outbreaks of CA-MRSA skin and soft tissue infections have occurred in metropolitan areas throughout the country including San Francisco¹¹, Boston¹² and Dallas¹³. These outbreaks have identified key risk differences for CA-MRSA colonization and/or infection among this population

Date: 6/10/13

Principal Investigator: [name], MPH, NP

Application Number: NA_00079147

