Randomization: This study has taken into consideration the guidelines for reporting of clinical trials as recommended by the CONSORT report²¹ to inform the study design (Figure 1). After recruitment and informed consent, patients will undergo pre-randomization screening. Patients who screen negative for MRSA at this point will have completed the protocol. Patients screening MRSA positive will then be randomized to the two possible open-label treatment arms. Arm 1 will include randomization to standardized decolonization protocol of the individual plus household and/or sexual partner(s). Arm 2 will include randomization to standardized decolonization protocol for the individual patient alone. Randomization will occur through computerized random number generation in Stata, version 11. A simple parallel randomization design will be utilized. Once developed, this randomization scheme will be placed in an individually concealed envelope. The RA will not be aware of the randomization scheme of the individual envelopes until opened in front of the patient on the day of randomization.

Figure 1: SUSTAIN Study Design Overview

* The household members and/or sexual contacts will be consented prior to initiation of the decolonization protocol

Data Collection Measures:

The risk factor questionnaire used in the proposed study has been thoroughly evaluated with over 1000 subjects (50% with HIV). Questions have been added or removed as applicable to this patient population. The

Date: 6/10/13

Principal Investigator: [name], MPH, NP

Application Number: NA_00079147

questions in the protocol can easily be administered by a study team member in 20 minutes. The questionnaire has been thoroughly evaluated by experts in the field of hospital epidemiology and infection control for content validity. In addition to the subject questionnaire, each instrument contains an additional section for the research team to interrogate the patient's medical record to verify specific pieces of the medical history such as CD4 count, medication history, viral load, etc. Adolescents will complete the questionnaire, but for children younger than 13, we will have the parent complete the risk factor questionnaire. Each document ends with a microbiology results page for the principle investigator (PI) to complete.

MRSA Screening Procedures:

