We will utilize the following microbiologic procedures: Following the current gold standard, each swab will be streaked onto CHROMagar-MRSA (BD Diagnostics, Inc.) a selective MRSA medium, and then placed in Trypticase soy broth (TSB) with 6.5% NaCl²² to enhance Staphylococcal identification. CHROMagar-MRSA plates are incubated at 35°C and reviewed at 24 hours. Mauve colored colonies on CHROM-MRSA will be confirmed as *S. aureus* (SA) by Gram stain and latex agglutination (Staphaurex Plus [Remel, Lenexa, KS]). All MRSA isolates will then undergo molecular characterization using pulse-field gel electrophoresis (PFGE), a molecular epidemiologic approach that facilitates identification of patterns in the genetic structure of bacteria to determine if transmission has occurred. Our team has extensive experience with this molecular typing mechanism.

FOLLOW-UP:

Patient Evaluation Time Points: After informed consent, each subject will undergo pre-randomization MRSA screening followed by completion of a risk factor screening questionnaire as part of the baseline visit. Results of these tests will be available in 24 hours. After culture results are available, the study team will randomize the subject and provide the required decolonization materials and schedule a start date. For individuals randomized to the arm including their household members/sexual partner, a date will be scheduled to visit the home or CRU. Once the decolonization protocol is complete, a follow-up MRSA screening assessment and adherence evaluation will occur (Visit #1). All subjects will be provided personal hygiene and household cleaning instructions. Based on this date, the research assistant will determine the date of the 3 (Visit #2) and 6 (Visit #3) month follow-up for subsequent risk factor and microbiologic evaluation. Study visits and variables collected at each visit are summarized in table 1.

Table 1: Timeline for Study Data Collection and Assessments for all participants

	Baseline	Visit 1	Phone	Visit 2	Phone	Visit 3
Data to be collected	Pre-	Post-		3		6

Date: 6/10/13

Principal Investigator: [name], MPH, NP

Application Number: NA_00079147

	Screening and Consent	decolonization MRSA Screening	check- in	month	check- in	month
Full ACASI Risk Factor Questionnaire	X					
Abbreviated ACASI Risk Factor Questionnaire				X		X
MRSA Screening	X	X		X		X
Molecular Evaluation	X					X
Telephone contact for appointment reminder			X		X	

5. Inclusion/Exclusion Criteria

Eligibility Criteria:

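### The 6-month outcome is dated from completing decolonization, so a randomized index who does not complete has no defined swab date, and Arm 1 has an extra route to that

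*Combined protocol and SAP*

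**What the plan says.** **Randomization.** Section 4, Allocation, randomizes the index once the pre-randomization screen is positive: "Patients screening MRSA positive will then be randomized to the two possible open-label treatment arms". The contacts' participation is not a condition at that point.

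**Contacts.** They come in through the index: "Recruitment of the primary sexual partner and or family members will occur by referral from the enrolled subject" (Section 5). The Figure 1 note adds: "The household members and/or sexual contacts will be consented prior to initiation of the decolonization protocol". Under Study initiation after screening (Section 4), an Arm 2 index starts after learning the culture results. For Arm 1, a contact screening visit is arranged after assignment, within 14 days of those results, and household members then start together. Contacts in both arms are offered screening, but only in Arm 1 is it placed before the start of treatment.

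**Visit clock.** The Follow-up text sets the first post-treatment visit by completion ("Once the decolonization protocol is complete, a follow-up MRSA screening assessment and adherence evaluation will occur (Visit #1") and continues: "Based on this date, the research assistant will determine the date of the 3 (Visit #2) and 6 (Visit #3) month follow-up". Aim 1 matches, looking for "lower occurrence of MRSA colonization at 6 months after completion of decolonization protocol". The schedule is headed "Table 1: Timeline for Study Data Collection and Assessments for all participants" but offers no other anchor. The same Follow-up text also says, without separating the arms, that once cultures are back the team randomizes, hands out materials and schedules a start date.

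**Analysis.** Section 7 compares the 6-month proportions by Fisher's exact test and adds multinomial regression. In the text available it names no analysis population and no handling of missing 6-month swabs beyond a 20% attrition allowance.

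**The concern.** The primary outcome hangs on an event after randomization, completion of the regimen, that need not happen and can fail differently in the two arms. Non-completers in either arm are left without a date. In Arm 1 a further step, involving people other than the patient, lies between allocation and start. Section 5 requires contacts to consent and to be free of allergy to the agents, without saying what follows for the index if they do not or are not. The Limitations in Section 7 (item 4) accept that not every contact can be reached.

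If staff take this to mean that such an index does not start, no completion date arises and no 6-month swab falls due. Choosing later to analyse everyone as randomized cannot recover a swab that was never scheduled. Arm 1 would then keep mainly indexes with cooperative contacts, while Arm 2 would not be filtered this way. In an open-label trial that compares a selected group with an unselected one. It would also distort the quantity that Aim 2 sets out to obtain: "To estimate the intervention effect size and develop an intervention fidelity assessment plan to scale the intervention into a larger multi-city R01 application".

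**Working it through.** **1. The plan's own figure.** Inputs from Section 7: 60% colonized in Arm 2, 30% in Arm 1, alpha 0.05 (taken as two-sided), about 80% power, 41 per arm, raised to 50 for attrition. For two proportions with pooled null variance,

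n = [1.960·√(2p̄(1−p̄)) + 0.842·√(p₁(1−p₁) + p₂(1−p₂))]² / (p₁−p₂)².

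With p₁ = 0.60, p₂ = 0.30 and p̄ = 0.45 this gives 41.97, so 42 per arm; power at 41 is 79.0%. The stated figure is reproduced and is not in dispute.

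**2. When is the 6-month date defined?** From the text in Section 4:

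| Index | Arm 2 | Arm 1 |
|---|---|---|
| Completes the regimen | Defined | Defined |
| Never starts or never completes | Not defined | Not defined |
| Contacts decline, are allergic or are not reached | Does not affect the start | No rule: dated if the index completes alone, otherwise not |

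The second row is certain. The third row, in Arm 1 only, is open.

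**3. Illustration of size.** Assumptions, none of them from the documents: a share q of Arm 1 indexes has no participating contact; they carry the Arm 2 risk of 0.60, since no contact is treated; the others carry 0.30; and all affected indexes are lost.

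- Arm 1 risk over all randomized = 0.30(1−q) + 0.60q.
- Effect over all randomized = 0.60 minus that risk. If the affected indexes are lost, the trial reports 0.60 − 0.30 = 30 points.

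| q | Arm 1 risk | Effect, all randomized | Overstatement | n per arm for that effect | Power of a later trial with 42 per arm |
|---|---|---|---|---|---|
| 10% | 0.33 | 27 points | 3 points | 53 | 0.71 |
| 20% | 0.36 | 24 points | 6 points | 67 | 0.60 |
| 30% | 0.39 | 21 points | 9 points | 88 | 0.49 |

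The last two columns use the formula in step 1; 42 per arm is what a successor would choose if it believed the 30 points.

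**4. If there is no true effect.** Let both arms have risk 0.60 and the lost Arm 1 indexes have risk r of 0.70 or 0.80. The retained Arm 1 risk is (0.60 − q·r)/(1 − q). Take 40 in Arm 2 (50 less 20%) and 40(1−q) = 36, 32 or 28 in Arm 1, so this loss comes on top of the planned attrition. The spurious benefit runs from 1.1 points (q = 10%, r = 0.70) to 8.6 points (q = 30%, r = 0.80). Exact rejection rates of the two-sided Fisher test:

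| q | r = 0.70 | r = 0.80 | No selection, same sizes |
|---|---|---|---|
| 10% | 3.7% | 3.9% | 3.6% |
| 20% | 3.9% | 5.1% | 3.5% |
| 30% | 5.2% | 9.1% | 4.0% |

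Only the extreme cell clearly exceeds 5%.

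**The case against.** A reader might infer that an Arm 1 index whose contacts do not take part is withdrawn, or certainly has no 6-month outcome. The documents do not support that. The Follow-up text gives materials and a start date without limiting this to one arm, so such an index could complete alone and be dated from there. Section 4 already leaves an Arm 1 index with only uncolonized contacts as the sole person treated, since those contacts receive no regimen. The common start for household members sets timing; it does not bar the index from starting. No text removes an index, and the schedule of assessments covers all participants. This part of the objection stands: the Arm 1 route is a gap in the rules, not a stated exclusion.

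Eligibility also screens out some of the problem. The index must have at least two household members and/or a partner, and must be willing to be randomized to household or partner evaluation. That tests the index's willingness, however, not the contacts'.

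The figures are open to fair criticism as well. The 10-30% rate is assumed, and so is total loss. Section 7 gives 30% as the risk for the whole of Arm 1. The illustration assigns it to participating households only, including those whose contacts are uncolonized and so untreated. If 30% is the whole-arm risk, neither the overstatement nor the power figures apply.

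Finally, the missing name for the analysis population would by itself be only missing detail, and Figure 1 could be read only through its note. What the objection does not remove is the completion anchor itself, which leaves non-completers undated in both arms.

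**Conclusion.** The concern holds in a limited form. It is certain from the text that the 3- and 6-month visits run from completion of decolonization, and that a randomized index who never starts or completes has no defined 6-month date in either arm. It is also clear that Arm 1 alone has a contact visit between randomization and start, with no rule for its failure. Whether indexes would actually be lost that way is not settled by the documents.

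Under the stated assumptions the effect would be overstated by 3, 6 or 9 points at 10%, 20% or 30% non-participation. The main harm is to the effect estimate and to the later trial planned from it. A general claim of inflated type I error is not supported. This should be corrected before recruitment; confidence is medium, because the size depends on a rate that the documents do not give.

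**What to change.** 1. **Follow-up text, Section 4.** Keep completion dating for those who complete. At randomization, also fix a 3- and 6-month swab date for every index, by the same rule in both arms, to be used whenever no completion date exists. One possible rule counts from randomization plus 24 days (the 14-day contact window plus the 10-day course). Collect these swabs whatever the contacts do and however much of the regimen was taken.
2. **Statistical Analysis Plan, Section 7.** Compare all randomized indexes in their assigned arm, and state a rule or sensitivity analysis for missing 6-month swabs.
3. **Reconcile** the Randomization, Study initiation and Follow-up text in Section 4 with the eligibility text in Section 5 on what happens to an Arm 1 index whose contacts decline, are allergic or are not reached. That rule is for the trial team to decide.

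**Cost.** Text changes, and a few more follow-up contacts within visits already planned for 50 per arm: 5 to 15 Arm 1 indexes at 10-30% of 50, plus any other non-completers. The estimated effect of the strategy as offered may be smaller. Under the assumptions in step 3, exact Fisher power at 40 per arm falls from 0.72 to 0.62, 0.51 or 0.40; if 30% is the whole-arm risk, it stays at 0.72.
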